## 5.2 Screening and Baseline Characteristics

Summary tables will be constructed for the following screening or pre-dose data and summarized by treatment group: demographic characteristics of age, sex, race, ethnicity, weight, height and body mass index (BMI), medical history, prior and concomitant medications, laboratory examinations, vital signs, and ECG for the safety population.

Medical history will be coded with the Medical Dictionary for Regulatory Activities (MedDRA, version 23.1 September 2020) terminology. Prior and concomitant medications will be summarized by World Health Organization Drug Dictionary Anatomical-Therapeutic-Chemical classification and preferred term (September 2020 version). Medical history and prior and concomitant medications will be summarized for the Safety Population.

Listings will be provided for eligibility criteria violations, demographics, medical history, and prior and concomitant medications.

## 5.3 Patient Disposition

The number and percentage of patients in each treatment group will be summarized for each investigative site (and combined) for each analysis population. The number and percentage of patients who are randomized, treated, prematurely discontinued (overall and by reason), and who complete the study will be summarized. The frequency and percentage of patients who withdraw or discontinue from the study, along with the reason for withdrawal or discontinuation, will be summarized by treatment. Individual patient dispositions will be provided by a listing.

All reported major protocol deviations and determined exclusions from any analysis population(s) will be provided in a listing.

## 5.4 Efficacy Analyses

### 5.4.1 Primary Analysis

The primary efficacy endpoint will be the change in PANSS total score at Week 12 from Baseline. A mixed model for repeated measures (MMRM) will be used to

assess treatment group differences for change from baseline. Fixed effects will include treatment group, analysis visit, treatment-by-visit interaction, and a baseline-by-visit interaction. Visit will be fit as a repeated effect using the repeated statement in SAS. The baseline score will be included as a continuous covariate. An unstructured covariance structure and Kenward-Roger degrees of freedom will be used. In the event an unstructured covariance structure fails to converge, a Toeplitz structure will be used.

Least squares means will be presented for treatment\*visit, with the significance level of the treatment-by-visit interaction presented in summary tables. Pair-wise comparisons of differences in LS means, two-sided 95% confidence intervals (CIs) on differences, and p-values will be provided for each active treatment versus placebo for each visit.

A listing for PANSS individual questions as well as subscale totals will be provided.

#### **5.4.2 Secondary Analyses**

Change in CGI-S score and PSP score at Week 12 from Baseline will be evaluated as secondary endpoints.

MMRM analyses, as described for the primary analysis, will be conducted on the change scores for the CGI-S and PSP. Individual patient scores for the CGI-S and PSP will be provided in listings.

#### **5.4.3 Exploratory Analyses**

The following exploratory analyses will be conducted using MMRM as specified above:

- Change in PANSS total score at Weeks 2, 4, 8 and 10 from Baseline
- Change in PANSS Positive Symptoms Factor Score (PSFS; items P1-P7) at Weeks 2, 4, 8, 10, and 12 from Baseline
- Change in PANSS Negative Symptoms Factor Score (NSFS; items N1-N7) at Weeks 2, 4, 8, 10, and 12 from Baseline
- Change in General Psychopathology Symptoms Factor Score (items G1-G16) at Weeks 2, 4, 8, 10 and 12 from baseline
- Change in PANSS Cognitive Symptoms (items P2, N5, G5, G10, G11) at Weeks 2, 4, 8, 10, and 12 from Baseline
- Change in Marder Negative Symptoms Factor Score (Marder NSFS; items N1, N2, N3, N4, N6, G7, G16) at Weeks 2, 4, 8, 10, and 12 from Baseline
- Change in PANSS total score at Week 12 from the average of the Screening, Qualification, and Day 1 pre-dose assessments
- Change in CGI-S score at Weeks 2, 4, 6, 8, and 10 from Baseline

- Change in PSP score at Week 6 from Baseline
- Change in Schizophrenia Quality of Life (SQLS) at Week 12 from Baseline

## 5.5 Safety Analyses

All safety summaries will be descriptive with no statistical hypothesis testing and based on the Safety Population. Patients will be summarized according to the study medication received (i.e., as treated), should it differ from the randomized treatment arm. All safety endpoints will be listed in by-patient data listings.

Adverse events (AEs) will be coded using the Medical Dictionary for Regulatory Affairs (MedDRA version 23.1 coding system and summarized by system organ class and preferred term. Clinically significant deteriorations in physical examination findings will be reported and summarized as adverse events. Abnormal, clinically significant laboratory values will be reported and summarized as adverse events.

### 5.5.1 Adverse Events

An adverse event reported after informed consent, but before the first dose of Study Medication (i.e., Day 1), will be considered a pre-treatment adverse event. These will be listed. Treatment-emergent adverse events (TEAEs) will be defined as any adverse event that occurs after administration of the first dose of Study Medication or AEs noted prior to the first Study Medication administration that worsen after Baseline. Individual patient TEAEs will be provided in a listing.

The number and percentage of patients who report TEAEs will be summarized by system organ class and preferred term. Treatment emergent adverse events will also be summarized by severity (mild, moderate, severe) as well as relationship to Study Medication (possibly, probably, or definitely related, unlikely related, or not related).

Patients who report the same preferred term on multiple occasions will be counted once for the preferred term under the highest severity when summarized by severity and under the closest relationship to Study Medication when summarized by relationship. If a patient reports multiple preferred terms for a system organ class, the patient will be counted only once for that system organ class.

Proportions for adverse events that are gender-specific (e.g., dysmenorrhea) will be based on the number of patients from that gender.

The number and percentage of patients who experience TEAEs will be summarized by treatment group for the following:

- By system organ class and preferred term
- By severity/intensity, system organ class, and preferred term

- By relationship to Study Medication (related, not related), system organ class, and preferred term
- Serious adverse events by system organ class and preferred term
- Serious adverse events by relationship to Study Medication, system organ class, and preferred term
- Adverse events resulting in discontinuation of Study Medication by system organ class and preferred term
- Adverse events that result in Study Medication dose interruption by system organ class and preferred term

By-patient listings will be provided for any deaths, serious adverse events, and adverse events leading to discontinuation of treatment.

A summary of adverse events will be provided in a table and will include numbers of subjects and percentages for following:

- Total TEAEs in each treatment group
- Number of patients with TEAEs
- Moderate or severe TEAEs (Grade 2 or above)
- Any related TEAE
- TEAEs leading to discontinuation
- Total SAEs
- Max severity of SAEs
- Any related SAE
- SAEs leading to discontinuation
- SAEs leading to death

Treatment-emergent adverse events that result in dose interruption (with subsequent resumption of dose) will also be identified.

### **5.5.2 *Columbia Suicide Severity Rating Scale***

The C-SSRS data will be summarized descriptively. Individual patient data will be provided in a listing. Only the following specific suicidal ideation and behavior category questions with any “Yes” responses will be summarized in a frequency distribution table at each post-randomization visit:

- Any Suicidal Ideation Category:
  - Wish to be Dead
  - Non-Specific Active Suicidal Thoughts

- Active Suicidal Ideation with Any Methods (Not Plan) without Intent to Act
- Active Suicidal Ideation with Some Intent to Act, without Specific Plan
- Active Suicidal Ideation with Specific Plan and Intent
- Any Suicidal Behavior Category:
  - Completed Suicide
  - Non-Fatal Suicide Attempt
  - Interrupted Attempt
  - Aborted Attempt
  - Preparatory Acts or Behavior
  - Any Suicidal Ideation or Behavior Category

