8. Patients who use prescription medications (stimulants) to treat attention deficit hyperactivity disorder or attention deficit disorder.
9. Screening laboratory measurements outside the normal range associated with potential risk for the treatment under investigation at the first Screening Visit (Week -5). This will include but not limited to:
 - a. Aspartate transaminase (AST), alanine transaminase (ALT), gamma-glutamyl transferase (GGT), or total bilirubin > 2x upper limit of normal (ULN)
 - b. Estimated glomerular filtration rate (eGFR) < 60 mL/minute/1.73 m²
 - c. Serum creatinine and/or blood urea nitrogen (BUN) > ULN
 - d. Urinalysis positive for protein or urine microalbumin/creatinine ratio (UACR) > 30 mg/g

Note: These laboratory tests may be repeated once, if they are abnormal on first screening, and if there is a medical/analytical reason to believe the results may be inaccurate. If the repeat test is within the reference range, the patient may be included only if the Investigator considers that the previous finding will not compromise the patient's safety and will not interfere with the interpretation of safety data.

10. Patients with suicidal behavior occurring within the past year or who pose a current suicide risk as determined by the PI or as confirmed at the first Screening Visit (Week -5), the Qualification Visit (Week -3) or Day 1 by affirmative answer on items 4 or 5 on the Columbia-Suicide Severity Rating Scale (C-SSRS).

11. Treatment with an investigational drug within 7 weeks or 5 half-lives (if known), whichever is longer, prior to the first Screening Visit (Week -5).
12. Donation of blood within 4 weeks of Day 1.
13. History of prolonged QT syndrome or a Screening QTc interval with Fridericia's correction (QTcF) > 450 msec for males or QTcF > 470 msec for females.
14. Females who are nursing, pregnant, or planning to become pregnant while in the study and for 4 weeks after the last dose of Study Medication.
15. History of meeting DSM-5 criteria for moderate to severe alcohol or substance use disorder (other than nicotine or caffeine) within the 6 months before the first Screening Visit (Week -5).
16. Positive alcohol breath test.
Note: A repeat alcohol breath test will be allowed within 48 hours of the first test only at the first Screening Visit (Week -5). The repeat test must be negative for inclusion in the study.

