8.2. Study Procedures

8.2.1 Screening Period Procedures (Week -5 and Week -3)

Prior to performing any study-related activities or evaluations, the patient must be thoroughly informed about all aspects of the study, including scheduled visits and activities. Patients will sign the study-specific consent form(s) prior to any screening procedure. Patients will be instructed to report all AEs that occur during the study from the time of informed consent forward.

Due to the COVID-19 pandemic and the possibility for site closures and/or travel restrictions, some Screening Period procedures (with the exception of PANSS) such as the MINI, medical history, review of concomitant medications) may be conducted remotely per Investigator discretion. The consent process must be conducted in the clinic and patients must sign the ICF in person in the clinic.

Patients should continue to take their prescribed AP medication throughout the Screening and Treatment Periods.

The following procedures will be performed at **Week -5**:

- Assessment of eligibility according to inclusion/exclusion criteria
- Conduct psychiatric evaluation and administer MINI International Neuropsychiatric Interview Psychotic Disorders, version 7.0.2 (MINI, Version 7.0.2; see [APPENDIX L](#))
- Demographics, medical history, including query for baseline signs/symptoms (ie, an AE with onset prior to dosing is to be recorded as a pretreatment AE)
- Review of concomitant medications including stable background AP therapy
- Full physical examination plus height and weight
- Vital signs including blood pressure, pulse rate, respiratory rate, and temperature
- Standard 12-lead ECG
- Urine pregnancy tests for women of childbearing potential
- Alcohol breath test
 - *A repeat alcohol breath test will be allowed within 48 hours of the first test. If the repeat test is positive, the patient must be excluded from the study*
- PANSS
- Assessment of suicidal ideation using C-SSRS (Baseline/Screening version)
- Serology, FSH, serum chemistry, hematology, and coagulation parameter evaluations
- Serum renal parameters and urinalysis

- Urine drug test
 - *Patients with a positive urine drug screen for benzodiazepines may be allowed in the study provided the drug was prescribed by a physician as an anxiolytic or sleep aid*
 - *Use of THC/cannabinoid products is allowed in the study*

The following procedures will be performed at **Week -3**:

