9.2. Exclusion Criteria

1. Patients with DSM-V criteria at the first Screening Visit (Week -5) for disorders other than schizophrenia that in the opinion of the Investigator may interfere with study conduct and interpretation of results.
2. Patients who, in the opinion of the Investigator, have a history of antipsychotic treatment resistance.
3. Patients currently taking clozapine.
4. Patients who have been previously treated with or are receiving electroconvulsive therapy (ECT).
5. Patients who have initiated or changed dose of antidepressants or other mood stabilizers within 7 weeks prior to the first Screening Visit (Week -5).
6. Patients currently taking lithium.
7. Patients taking an AP (e.g. Seroquel) as a sleep aid.

Note: Patients will be allowed to switch to a non-AP sleep aid during the Screening period.

8. Patients who use prescription medications (stimulants) to treat attention deficit hyperactivity disorder or attention deficit disorder.
9. Screening laboratory measurements outside the normal range associated with potential risk for the treatment under investigation at the first Screening Visit (Week -5). This will include but not limited to:
 - a. Aspartate transaminase (AST), alanine transaminase (ALT), gamma-glutamyl transferase (GGT), or total bilirubin > 2x upper limit of normal (ULN)
 - b. Estimated glomerular filtration rate (eGFR) < 60 mL/minute/1.73 m²
 - c. Serum creatinine and/or blood urea nitrogen (BUN) > ULN
 - d. Urinalysis positive for protein or urine microalbumin/creatinine ratio (UACR) > 30 mg/g

Note: These laboratory tests may be repeated once, if they are abnormal on first screening, and if there is a medical/analytical reason to believe the results may be inaccurate. If the repeat test is within the reference range, the patient may be included only if the Investigator considers that the previous finding will not compromise the patient's safety and will not interfere with the interpretation of safety data.

10. Patients with suicidal behavior occurring within the past year or who pose a current suicide risk as determined by the PI or as confirmed at the first Screening Visit (Week -5), the Qualification Visit (Week -3) or Day -1 by affirmative answer on items 4 or 5 on the Columbia-Suicide Severity Rating Scale (C-SSRS).
11. Treatment with an investigational drug within 7 weeks or 5 half-lives (if known), whichever is longer, prior to the first Screening Visit (Week -5).
12. Donation of blood within 4 weeks of Day 1.

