9.3. Patient Withdrawal Criteria

Patients may withdraw from participation in the study at any time. The Investigator may withdraw a patient at any time if they believe the safety of the patient or the integrity of the data are at risk. In addition, patients should be withdrawn if they:

- Experience a serious or intolerable AE
- Develop a clinically significant laboratory or ECG abnormality
- Develop proteinuria of 1-2+ or UACR > 30 mg/g as confirmed by a repeat lab test
- Develop eGFR levels < 60 mL/minute/1.73 m² as confirmed by a repeat lab test
- Develop *symptomatic* ALT or AST elevation ≥ 2 x the ULN on two repeat lab tests or develop *asymptomatic* ALT or AST elevation ≥ 3 x the ULN as confirmed by a repeat lab test
- Develop total bilirubin ≥ 2 x the ULN as confirmed by a repeat lab test
- Exhibit suicidal behavior as determined by an affirmative answer on items 4 or 5 on the C-SSRS
- Do not follow guidelines specified in the protocol (i.e., is noncompliant with protocol procedures or Study Medication administration) or specific instructions by the study staff
- Any medically appropriate reason or significant protocol violation, in the opinion of the Investigator
- Are lost to follow up

In case of two consecutive missed safety assessments due to the COVID-19 pandemic, continued patient participation in the study must be discussed by the Investigator and the Medical Monitor.

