#### **5.1.3 Statistical Analyses – General Considerations**

For the Treatment Period, data will be summarized by treatment group (CTP-692 1 g QD, CTP-692 2 g QD, CTP-692 4 g QD, or placebo). All data for analysis will be listed by patient.

The same number of decimal places as in the raw data will be presented when reporting minimum and maximum, 1 more decimal place than in the raw data will be presented when reporting mean and standard deviation.

Continuous variables will be summarized by treatment using descriptive statistics (n, mean, median, standard deviation, minimum, and maximum). For categorical variables, frequencies and percentages will be presented by treatment. Baseline is defined as the last observation prior to initiation of Study Medication.

Listings for CSR Appendix 16.2 will include all the patient data points being collected or derived for analyses. Data listings will be provided for all patients up to the point of study completion or withdrawal.

All statistical tests will be 2-sided with a significance value of 0.05. Patients will be summarized by randomized treatment group, except for the Safety Population, which will be summarized by actual treatment received. There will be no adjustments for multiple comparisons.

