**Table 2 – Guidelines for Assigning Unscheduled and Early Termination Visits for Efficacy Assessments**

Week/Visit	Time Interval (Day)	Target Time Point (Day)
-5/Screening	Use nominal	-35*
-3/Qualification	Use nominal	-24 to -21*
1 (Baseline/Day 1)	Last assessment prior to dosing	1
2	8 to 21	14
4	22 to 35	28
6	36 to 49	42

8	50 to 63	56
10	64 to 77	70
12	78 to 1 day prior to Safety Follow-up	84
13/Safety Follow-up	Use nominal	91

\*5-week Screening/Qualification Period may be extended up to 2 weeks if repeat laboratory test results for confirmation of eligibility are pending.

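### C-SSRS: the one table specified counts Yes answers visit by visit, so it gives neither the number of patients affected on treatment nor the number with new item 1-3 ideation

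*SAP*

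**What the plan says.** SAP 5.5.2 names the C-SSRS ideation and behaviour categories and states that Yes "responses will be summarized in a frequency distribution table at each post-randomization visit". Protocol 13.4.6 has the same plan. The last row pools all categories within a visit; it does not pool visits within a patient. SAP 5.5.2 also states: "Individual patient data will be provided in a listing". SAP 5.1.3 adds: "Listings for CSR Appendix 16.2 will include all the patient data points being collected or derived for analyses".

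The scale is given three times before dosing. Protocol 8.2.1 has "Assessment of suicidal ideation using C-SSRS (Baseline/Screening version" at Week -5, and the Since Last Visit form follows at Week -3 and Day 1. SAP 5.2 lists the pre-dose data to be tabulated and does not include the C-SSRS.

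Exclusion criterion 10 covers "Patients with suicidal behavior occurring within the past year or who pose a current suicide risk as determined by the PI", or risk shown "by affirmative answer on items 4 or 5 on the Columbia-Suicide Severity Rating Scale (C-SSRS" at a pre-dose visit. Ideation on items 1, 2 or 3 is not in itself an exclusion.

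**The concern.** Suicidality is a named safety measure (protocol 6, SAP 2.4). Two figures are needed to compare the arms: how many patients had ideation or behaviour at any time after the first dose, and how many were worse than before dosing. The specified table gives neither.

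Other safety summaries in the same SAP do have these features. Treatment-emergent adverse events are defined against baseline and counted once per patient and preferred term (5.5.1). The laboratory table of clinically significant values requires a lower grade at baseline (5.5.3). QTcF outliers are taken over all post-baseline visits and must exceed the patient's own baseline (5.5.6). The adverse event tables are not an assured substitute for a C-SSRS count: no rule turns a C-SSRS Yes into an adverse event, and worsening of the condition under study is not one (4.5.1).

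**Working it through.** **Inputs.** The plan states no C-SSRS rate, so it has no figure of its own to reproduce here. The post-dose C-SSRS visits are Weeks 2, 4, 6, 8, 10 and 12, six in all (SAP Table 1). About 75 patients per arm are randomized and about 60 are expected to complete (SAP 5.1.1).

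**Step 1: distinct patients behind the visit counts.** If the table shows y Yes answers at each of V visits, the number of distinct patients lies between y (the same patients throughout) and V × y (different patients each time).

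- y = 1, V = 6: 1 to 6 patients; 1/75 = 1.3%, 6/75 = 8.0%.
- y = 3, V = 6: 3 to 18 patients; 3/75 = 4%, 18/75 = 24%.

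The denominator is held at 75 for simplicity. With 60 patients at Week 12 the percentage there would be 1/60 = 1.7% rather than 1.3%, but the uncertainty in the number of patients is the same.

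**Step 2: what a post-dose Yes means, by category.**

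| Category | Permitted at entry? | Post-dose Yes in the by-visit table |
|---|---|---|
| Ideation items 1-3 | Yes, unless the investigator judges the patient a current risk | New or continuing; the table does not show which |
| Ideation items 4-5 | No | New relative to entry |
| Suicidal behaviour | Not within the past year | New relative to entry |

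The post-dose form asks about the time since the last visit. It therefore excludes lifetime history, but it does not show whether the ideation was already there before dosing.

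**Step 3: effect of entry ideation on an arm comparison (assumed rates).** Let p be the share of each arm entering with item 1-3 ideation that persists, and q the rate of new ideation in the rest. The share with any post-dose Yes is p + (1 − p)q. Take q = 2% on placebo and 6% on active, a true ratio of 3.0.

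- p = 2%: 0.0396 and 0.0788, ratio 1.99.
- p = 5%: 0.069 and 0.107, ratio 1.55.
- p = 10%: 0.118 and 0.154, ratio 1.31.

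So a once-per-patient count without a pre-dose reference would still dilute a difference. Both are needed.

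**Step 4: unscheduled and Early Termination assessments.** The text of SAP 5.1.5 allocates data from these visits to windows in general terms, but it points to a table titled "Guidelines for Assigning Unscheduled and Early Termination Visits for Efficacy Assessments". Whether the windows govern the C-SSRS is not clear. If they do, an unscheduled assessment is used for a completer only when the scheduled one is missing. If they do not, the SAP gives no column for it.

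**The case against.** The strongest reply is that nothing is lost. The listing holds every pre-dose and post-dose answer, events are likely to be few, and a reader can trace each patient. All safety summaries are descriptive (SAP 5.5). Mock shells and the list of tables are separate documents and may change without a SAP update (SAP 1 and 7), so a suitable table may exist there. Those documents were not available.

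Much of this stands. A reader might infer that new suicidality cannot be identified at all; the listing rules that out, and the overlap with entry is confined to items 1-3. A reader might also take the word only in SAP 5.5.2 to forbid any other summary; it limits which questions are tabulated, not how. Nor is it right that no table counts patients: each by-visit frequency does so within its visit.

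What the reply does not answer is prespecification. With a listing alone, the reference period and the counting rule would be chosen after unblinding.

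**Conclusion.** The point holds as a gap in the specified tabulation. From the table in SAP 5.5.2 and protocol 13.4.6 one cannot obtain the number of distinct patients per arm with ideation or behaviour on treatment, nor separate new item 1-3 ideation from that permitted at entry. The six-fold range (1 to 6 patients, 1.3% to 8.0% of 75) and the diluted ratios are illustrations on assumed inputs, not estimates for this trial.

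Two further inferences are tempting but not supported. Protocol 9.3 lists for withdrawal patients who exhibit suicidal behaviour "as determined by an affirmative answer on items 4 or 5 on the C-SSRS", and a reader might conclude that the Week 12 column is emptied of the most serious cases. But their Yes is counted at the visit where it occurred, early leavers should have the Week 12 assessments, and the SAP states no denominator for this table. A reader might also conclude that Early Termination and unscheduled C-SSRS data are left out; the documents show only that their placement is ambiguous.

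Efficacy inference is unaffected.

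**What to change.** Add to SAP 5.5.2 one table by arm, on the Safety Population:

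1. The number and percentage of patients with each ideation category, each behaviour category, and any of them, at any assessment after the first dose. Include unscheduled and Early Termination assessments and count each patient once.
2. A shift from the worst pre-dose category to the worst post-dose category.

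Define the pre-dose reference in the SAP as the Week -3 and Day 1 Since Last Visit forms taken together. The general baseline in SAP 5.1.3, the last observation before dosing, would use Day 1 alone and miss ideation reported at Week -3. Add the recent-period column of the Week -5 form only once its look-back is stated; the form in protocol Appendix J leaves the number of months as an unfilled X. State also whether the Table 2 windows apply to the C-SSRS in the by-visit table, and keep that table as supportive.

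The cost is SAP wording and one extra descriptive table with small counts, from data already collected. The pre-dose reference covers about 5 weeks (up to 7 if qualification is extended) against 12 weeks of treatment, so some worsening can be expected in every arm and the shift should be read against placebo.
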